9.4.2.3.2 Adverse Events

Subject incidence of all **treatment-emergent adverse events** will be tabulated by system organ class and preferred term. Tables of fatal **adverse events**, **serious**

Date: 21 April 2022 Page 68 of 108

adverse events, adverse events leading to discontinuation from investigational product or other protocol-required therapies, and significant treatment-emergent adverse events (including adverse events of interest [EOIs]) will also be provided. These analyses will be performed using subjects in the SAS. Analysis will be repeated for treatment-emergent adverse events during MDMP using the PAS.

Subject incidence of device-related events, if applicable, will be tabulated by system organ class and preferred term.

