4.2 Subgroups

Due to small sample size, subgroup analysis will not be performed.

5. Definitions

Age at Enrollment:

Subject age at enrollment will be collected in years in the clinical database.

Adverse Event During the MDMP

Adverse event during the MDMP is defined as an adverse event that started within 72 hours after the first dose of blinatumomab in cycle 1 and within 48 hours after the first dose of blinatumomab in cycle 2.

For adverse events with missing start time, the adverse event during the MDMP is defined as an adverse event that started within 3 days after the first dose date of blinatumomab in cycle 1 and within 2 days after the first dose date of blinatumomab in cycle 2.

Baseline

The baseline value will be defined as the value measured on day 1 of the first cycle before start of the first infusion of blinatumomab. If a cycle 1 day 1 value is not available, the latest value before the day 1 of the start of blinatumomab infusion may be used.

Cumulative Dose of Blinatumomab

The cumulative dose in μg is defined as the following with summation over infusions:

 \sum Duration of infusion [days] for each dose received × dose received [μ g/day].

Cumulative dose will be calculated within a cycle and across all cycles.

Duration of Therapy

For each infusion episode within a cycle, the duration of exposure will be calculated by subtracting the start date and time from the stop date and time. If either a start or stop time is missing, only the date portion will be used in calculating the duration of a specific

infusion. For each cycle, the duration will be the sum of the individual infusion durations within that cycle. For the entire study, the duration will be the sum of the durations across cycles. The duration will be rounded to the nearest day.

End of Study

The end of study date is defined as the date when the last subject across all sites is assessed or receives an intervention for evaluation in the study (i.e. last subject last visit).

End of Study Visit

The end of study visit will occur 30 days (\Box 3 days) after the last dose of blinatumomab is given. The end of study visit will occur after cycle 3 or 4 for subjects who chose these optional cycles. End of study visit date for each subject will be recorded on the End of Study CRF page.

Enrollment Date

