6.2 Safety Analysis Set (SAS)

Safety analysis set will include all enrolled subjects who receive at least 1 dose of blinatumomab. The analysis of secondary safety and resource utilization endpoints will be conducted on the SAS.

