9.6.2 Adverse Events

The Medical Dictionary for Regulatory Activities (MedDRA) version 25.0 or later will be used to code all events to a system organ class (SOC) and a preferred term (PT). Severity will be coded by using CTCAE version 5.0 or later.

Subject incidence of all, serious, grade 3 and above, leading to withdrawal of investigational product, leading to interruption of investigational product, fatal, treatment-related, treatment-related serious, and treatment-related grade 3 and above TEAEs will be tabulated by SOC and PT in descending order of frequency. In addition, treatment-emergent adverse events will be summarized by SOC, PT, and grade; and by PT only in descending order of frequency.

Treatment-emergent events of interest (EOIs) will be summarized by EOI category and preferred term. In addition, for each EOI category, the subject incidence of all, serious, grade 3 and above, grade 4 and above, fatal, leading to withdrawal of IP, leading to interruption of IP will be summarized. Time to onset, duration, number of resolved events for select EOIs (infection, neurologic events and CRS) will also be summarized.

To support estimation of healthcare resource utilization associated with treatment-related AEs, the summary of subject incidence treatment related TEAEs will be provided for treatment related TEAEs that resulted in hospitalizations, treatment related TEAEs that resulted in surgeries, treatment related TEAEs that resulted in the use of concomitant medications, treatment related TEAEs that resulted in the use of device/procedure intervention (see SAP section 10 'Changes from Protocol-specified Analyses' for details on updates to endpoints of secondary objective for estimation of healthcare resource utilization).

The above analyses will be performed using subjects in the SAS.

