9.6.8 Exposure to Investigational Product

Descriptive statistics will be produced to describe the exposure to blinatumomab for subjects in the SAS. The duration of therapy and the cumulative dose will be summarized.

The number and percent of subjects with dose modifications (eg, dose changes, dose interruptions) and reason for modification will be summarized. Analysis will be repeated for exposure during MDMP.

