9.7.4 Analyses of Biomarker Endpoints

Not applicable.

10. Changes From Protocol-specified Analyses

For estimation of secondary objective on healthcare resource utilization, the endpoints are updated to treatment-related TEAEs instead of the TEAEs in consistency with the objective.

CAD Costion	Iludete
SAP Section	
Section 2.1	a) The wording of below primary and secondary endpoints
	from protocol are modified in the SAP to clarify what
	endpoints are exactly evaluated at the subject level:
	Primary endpoint: Incidence of grade 3 and/or 4 CRS,
	NT or any adverse event (AE) requiring hospitalization
	(SAE) during MDMP
	Secondary endpoint: Overall incidence and severity of
	treatment-emergent adverse events (TEAE) and adverse
	events of interest in particular CRS and NT
	b) For estimation of secondary objective on healthcare
	resource utilization, the endpoints are updated to include
	'treatment-related TEAEs' instead of the 'TEAEs' in
	consistency with the objective.
Section 8.3	Subject replacement rule for analysis is updated to exclude the
	below criterion from protocol. Since the replacement rule is
	defined for analysis, an additional text on replacement status
	applicability for internal data analysis also excluded.
	Text from protocol section 4.2.1 excluded from SAP section
	8.3:
	Subjects are removed from treatment with IP due to disease
	progression.
	Replacement status is only applicable for internal data
	analysis.

11. Literature Citations / References

12. Prioritization of Analyses

Not applicable

13. Data Not Covered by This Plan

Not applicable.

14. Appendices

Appendix A Reference Values/Toxicity Graders Table 14-A. Summary of Potential Hy's Law Cases (Safety Analysis Set)

	Blinatumomab
	(N = XXX)
Pre-infusion - n/N1(%)	
ALT or AST >3xULN	xx/xxx (xx.x)

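### Two adverse-event outputs planned in the protocol (TEAEs during the MDMP on the PAS, and device-related events) are absent from the SAP and not listed among its changes

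*Protocol*

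**What the plan says.** Protocol 9.4.2.3.2 sets out the whole-study adverse-event tables on the SAS and then makes two further commitments. The first is a repeat for the monitoring window: "Analysis will be repeated for treatment-emergent adverse events during MDMP using the PAS". The second is conditional: "Subject incidence of device-related events, if applicable, will be tabulated by system organ class and preferred term".

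SAP 9.6.2 lists TEAE tables (all, serious, grade 3 and above, leading to withdrawal or interruption, fatal, treatment-related, and by grade), then EOI tables, then resource-use tables. It closes with "The above analyses will be performed using subjects in the SAS". This agrees with SAP 6.2: "The analysis of secondary safety and resource utilization endpoints will be conducted on the SAS".

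SAP Section 10 lists the changes from the protocol. It covers the rewording of two endpoints, the replacement rule, and the resource-use change, where "the endpoints are updated to treatment-related TEAEs instead of the TEAEs in consistency with the objective". It mentions neither the MDMP repeat nor the device-related table.

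**The concern.** The primary objective is the safety of outpatient dosing during the MDMP, with the CWHMS as the means of monitoring. The two outputs that did not reach the SAP are the ones that would describe adverse events in that window and adverse events attributed to devices.

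If the SAP is followed as written, the MDMP adverse-event result is one composite proportion. A reader could not see from the planned tables which event types started in the window, at what grade, or how often CRS and NT occurred below grade 3. Because Section 10 is silent, the reader also could not tell whether this was decided or overlooked.

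**Working it through.** This is mainly a comparison of texts. The SAP names a protocol dated 21 April 2022. That is the date of the current protocol (its Amendment 2, although the SAP calls it amendment 1), so the comparison is not with superseded text.

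| Output | Protocol | SAP |
|---|---|---|
| TEAE tables, whole study, SAS | Planned, 9.4.2.3.2 | Planned, 9.6.2 |
| TEAE tables, MDMP, PAS | Planned, 9.4.2.3.2 | Absent from 9.6.2 and 9.7; not in Section 10 |
| Device-related events by SOC/PT | Planned if applicable, 9.4.2.3.2 | Absent from 9.6.2 and 9.7; not in Section 10 |
| Exposure, MDMP repeat | Planned, 9.4.2.3.5 | Kept, 9.6.8 |
| Primary MDMP composite, exact CI, PAS | Planned, 9.4.2.3.1 | Kept, 9.6.1 |
| TTI and intervention types, PAS | Planned, 9.4.2.3.1 | Kept, 9.6.1, with alarm counts by reason |

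Four checks on whether the SAP supplies the missing outputs elsewhere:

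1. **The SAS rule.** SAP 6.2 cannot explain the omission. Protocol 9.3.1 also assigns secondary safety endpoints to the SAS, and the protocol still adds the MDMP repeat on the PAS.
2. **The MDMP definition.** SAP Section 5 says "Adverse event during the MDMP is defined as an adverse event that started within 72 hours" of the first dose in cycle 1, with a 48-hour window in cycle 2. No table in 9.6.2 uses this definition. The primary endpoint needs it anyway, so its presence does not show that MDMP tables are planned.
3. **Device wording.** The only device item in 9.6.2 is "treatment related TEAEs that resulted in the use of device/procedure intervention". That counts device or procedure use as a consequence of a treatment-related event. It does not count events caused by a device.
4. **Data.** Protocol Appendix 4 makes relatedness to the devices, including the CWHMS, a mandatory attribute of each AE, and onset is recorded. Both outputs can be produced from data already collected.

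The plan's own figures give the size:

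- Expected subjects with the composite: 0.38 × 45 = 17.1, which the plan rounds to 17.
- The exact (Clopper-Pearson) 95% interval for 17/45 is 23.8% to 53.5%. The upper limit averaged over Binomial(45, 0.38) is also 53.5%, so the plan's figure reproduces.
- Subjects without the composite: 45 − 17 = 28.

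For those 28, the MDMP incidence output records only that no composite event occurred. Grade 1–2 CRS or NT, and other grade 3 or higher events that did not lead to hospitalization, lie outside the composite. For the 17, SAP 9.6.1 does not plan a split into CRS, NT and hospitalization.

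**The case against.** The strongest reply is that the SAP keeps much of the MDMP safety information. It keeps the composite with an exact interval, TTI, interventions, and alarms by reason including a technical category. It keeps the MDMP repeat for exposure ("Analysis will be repeated for exposure during MDMP"). It plans time to onset, duration and number resolved for infection, neurologic events and CRS. The DRT also reviews safety after every fifth non-replaceable subject. The study is descriptive, and device-related TEAEs would still be counted in the general tables and be identifiable in the data.

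Most of this stands, and it limits the point. A reader might infer that the SAP removes the safety detail for the window altogether; the retained outputs show that it does not. They do not replace the missing tables, however. A time-to-onset summary gives no MDMP incidence by SOC/PT or grade. The SAP also does not state its time origin. If that is the first dose in cycle 1, an onset in the first two days of cycle 2 appears only as an onset at about six weeks. Alarm counts are not device-related AEs. A device effect arising during the screening wear test would not be treatment-emergent at all.

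A reader might also infer that whole-study tables dilute MDMP events in proportion to time, because the window is 5 of 56 infusion days in two cycles (5/56 = 8.9%) or 5 of 112 in four (5/112 = 4.5%). The documents do not support that. The planned tables report subject incidence, which does not scale with days. Protocol 2.3 says most AEs fell in the first few weeks of cycle 1, and the sample-size section assumes a 38% event rate within these 5 days alone.

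Finally, the protocol makes the device table conditional, so it cannot be called an unqualified requirement.

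**Conclusion.** The point holds as a protocol–SAP discrepancy with a specific loss. Two planned outputs are missing from the SAP and undisclosed in the section meant to disclose changes. Following the SAP leaves no SOC/PT, grade or EOI breakdown of TEAEs starting in the MDMP, and no tabulation of device-related AEs.

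The primary estimate and its interval are unaffected. The figure of about 28 subjects without the composite rests on the plan's 38% assumption and on 45 subjects in the PAS. The discrepancy does not depend on that figure.

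A reader might infer a deliberate decision to drop the tables. The documents do not show one. The retained MDMP definition and exposure repeat fit an oversight at least as well. In either case the SAP should be corrected before database lock, because these outputs bear directly on the window and the monitoring system under study.

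**What to change.** In SAP 9.6.2:

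- Restore the TEAE tables for AEs with MDMP onset, using the Section 5 definition, on the PAS. Rerunning the tables by SOC, PT and grade and the EOI tables with that filter shows grade 1–2 CRS and NT, and grade 3 or higher events without hospitalization. A separate grade 3 and above MDMP table is not needed to meet the protocol.
- Restore the table of device-related events by SOC and PT if any occur, and otherwise state that none did. The protocol does not name an analysis set for this table, so the SAP should.

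If either output is deliberately dropped, list it in Section 10 with the reason. A further MDMP repeat on the SAS, which would make replaced subjects visible, goes beyond the protocol and is optional.

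The cost is a few filtered reruns of tables already planned, with no new data collection.

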9.4.2.3.3 Laboratory Test Results

Summary statistics over scheduled visits for actual values and changes from baseline of selected laboratory parameters will be presented. In addition, shift tables between the post-baseline and baseline values for selected laboratory parameters will be provided. Subject incidence of potential cases of Hy's Law will be summarized.

9.4.2.3.4 Vital Signs

A summary of the subject incidence with abnormal changes in vital signs will be presented for subjects in the SAS. Vital signs to include: BP, **respiratory rate**, **pulse rate**, and axillary temperature.

9.4.2.3.5 Exposure to Investigational Product

Descriptive statistics will be produced to describe the exposure to blinatumomab for subjects in the SAS. The duration of therapy and the cumulative dose will be summarized. The number and percent of subjects with dose modifications (eg, dose changes, dose interruptions) and reason for modification will be summarized. Analysis will be repeat for exposure during MDMP.

9.4.2.3.6 Exposure to Other Protocol-required Therapy

Descriptive statistics will be produced to describe the exposure to required pre-medication (dexamethasone) in the SAS.

9.4.2.3.7 Exposure to Concomitant Medication

Number and proportion of subjects receiving therapies of interest will be summarized by preferred term as coded by the World Health Organization Drug dictionary in the SAS.

11.1 Appendix 1. List of Abbreviations and Definitions of Terms

Abbreviation or Term	Definition/Explanation
ADL	activities of daily living
AE	adverse event
ALL	acute lymphoblastic leukemia
Anti-HCV	hepatitis C virus antibody
ВСР	B-cell precursor
BiTE	bispecific T-cell engaging
ВМ	bone marrow
BP	blood pressure
BSA	body surface area
CAPA	corrective action/preventative action
CFR	U.S. Code of Federal Regulations
СН	Current Health
CiVI	continuous intravenous infusion
CNS	central nervous system
CR	complete remission
CRF	case report form
CRS	cytokine release syndrome
CSF	cerebrospinal fluid
CTCAE	Common Terminology Criteria for Adverse Events
CWHMS	Current Wearable Health Monitoring System
DILI	drug induced liver injury
DRT	data review team
ECG	electrocardiogram
ECOG PS	Eastern Cooperative Oncology Group Performance Status
EDC	electronic data capture
EFS	event-free survival
EMS	Emergency Medical Service
EOI	events of interest
EOS	end of study
EORTC	European Organisation for Research and Treatment of Cancer
ePRO	electronic patient reported outcomes
FDA	Food and Drug Administration
FSH	follicle stimulating hormone
GCP	Good Clinical Practice
GFR	glomerular filtration rate

Date: 21 April 2022 Page 73 of 108

GHS global health status

GvHD graft versus host disease

HCP healthcare provider

HBsAg Hepatitis B Surface Antigen
HIV human immunodeficiency virus

HR heart rate

HRT hormonal replacement therapy

HSCT hematopoietic stem cell transplantation

ICF informed consent form

ICH International Council for Harmonisation

ICU intensive care unit

IEC Independent Ethics Committee

IgG Immunoglobulin G
IP investigational product

IPIM Investigational Product Instruction Manual

IRB Institutional Review Board

IV intravenous(ly)
IVSS IV solution stabilizer

MDMP mandatory monitoring period

MRD minimal/measurable residual disease

NT neurotoxicity
OR operating room
OS overall survival

PAS primary analysis set

PCR polymerase chain reaction
Ph Philadelphia chromosome

PO oral(ly)

PRO Patient reported outcomes

QLQ-C30 Quality of Life of Cancer Patients

QoL quality of life

SAE serious adverse event
SAS Safety Analysis Set
SBP systolic blood pressure

SpO₂ peripheral capillary oxygen saturation

TBL total bilirubin

TEAE treatment-emergent adverse event

ULN upper limit of normal

US United States

Date: 21 April 2022 Page 74 of 108

WBC white blood cell count

Protocol Number: 20190014

Product: Blinatumomab

Date: 21 April 2022 Page 75 of 108

11.2 Appendix 2. Clinical Laboratory Tests

The tests detailed in Table 11-1 will be performed by the local laboratory.

Protocol-specific requirements for inclusion or exclusion of subjects are detailed in Section 5.1 to 5.2 of the protocol.

Additional tests may be performed at any time during the study as determined necessary by the investigator or required by local regulations.

Table 11-1. Analyte Listing

Local Laboratory: Chemistry	Local Laboratory: Coagulation	Local Laboratory: Urinalysis	Local Laboratory: Hematology	Other Labs
Sodium Potassium Chloride Albumin Total Calcium BUN Creatinine Glomerular filtration rate Uric acid Total bilirubin Direct bilirubin ALP LDH AST (SGOT) ALT (SGPT) Amylase Lipase	PT/INR aPTT	Blood Protein Glucose	RBC Hemoglobin Hematocrit Platelets WBC Differential • Absolute Neutrophils • Neutrophils • Segmented Neutrophils • Bands/stabs • Eosinophils • Basophils • Blasts • Lymphoblasts • Lymphoblasts • Lymphocytes • Monocytes • Myeloblasts • Promyelocytes • Myelocytes • Myelocytes • Myelocytes • Myelocytes • Atypical lymphocytes	Bone marrow histology and MRD CSF analytes • CSF Glucose • CSF Protein • CSF White Blood Cells • CSF Blasts Local Laboratory: Serum and/or Urine Pregnancy
			.,р.,.оо,.оо	

ALP = alkaline phosphatase; ALT = alanine aminotransferase; AST = aspartate aminotransferase; BUN = blood urea nitrogen; CSF = cerebrospinal fluid; INR = international normalized ratio; LDH = lactate dehydrogenase; MRD = minimal/measurable residual disease; PT = prothrombin time; aPTT = activated partial thromboplastin time; RBC = red blood cell count; SGOT = serum glutamic-oxaloacetic transaminase; SGPT - serum glutamic-pyruvic transaminase; WBC = white blood cell count

Date: 21 April 2022 Page 76 of 108

11.3 Appendix 3. Study Governance Considerations

Data Review Team

A data review team (DRT) is a group internal to Amgen, but external to the blinatumomab product team(s). The DRT will review accumulating safety data from the ongoing clinical trial to ensure no avoidable increased risk for harm to subjects. DRT review meetings will be triggered after the first occurrence of primary endpoint events and every 5 additional events thereafter

In order to maintain trial integrity, the unblinded data reviewed by the DRT will be restricted and not accessible by the Amgen product team.

The DRT is composed of members that are external to the study team and include a clinician, a safety physician, and a biostatistician. Membership, procedures, and meeting timing will be described in detail in the study DRT charter.

Regulatory and Ethical Considerations

This study will be conducted in accordance with the protocol and with:

- Consensus ethical principles derived from international guidelines including the Declaration of Helsinki and Council for International Organizations of Medical Sciences International Ethical Guidelines
- Applicable International Council for Harmonisation (ICH) Good Clinical Practice (GCP) Guidelines
- Applicable ICH laws and regulations

The protocol, protocol amendments, informed consent form (ICF), Investigator's Brochure, and other relevant documents (eg, subject recruitment advertisements) must be submitted to an Institutional Review Board (IRB)/Independent Ethics Committee (IEC) by the investigator and reviewed and approved by the IRB/IEC. A copy of the written approval of the protocol and ICF must be received by Amgen before recruitment of subjects into the study and shipment of Amgen investigational product (IP).

Amgen may amend the protocol at any time. The investigator must submit and, where necessary, obtain approval from the IRB/IEC for all subsequent protocol amendments and changes to the informed consent document. The investigator must send a copy of the approval letter from the IRB/IEC and amended protocol Investigator's Signature page to Amgen prior to implementation of the protocol amendment at their site.

Date: 21 April 2022 Page 77 of 108

The investigator will be responsible for the following:

 Providing written summaries of the status of the study to the IRB/IEC annually or more frequently in accordance with the requirements, policies, and procedures established by the IRB/IEC

- Obtaining annual IRB/IEC approval/renewal throughout the duration of the study.
 Copies of the investigator's reports and the IRB/IEC continuance of approval must be sent to Amgen
- Notifying the IRB/IEC of serious adverse events (SAEs) occurring at the site, deviations from the protocol or other adverse event reports received from Amgen, in accordance with local procedures
- Overall conduct of the study at the site and adherence to requirements of Title 21 of the U.S. Code of Federal Regulations (CFR), ICH guidelines, the IRB/IEC, and all other applicable local regulations

Recruitment Procedures

For sites that do not screen and/or enroll subjects, the Clinical Monitor will address concerns and identify any recruitment barriers with the investigator. Any potential subject recruitment materials used in this study must be submitted, reviewed and approved to the site IRB.

Informed Consent Process

The written ICF is to be prepared in the language(s) of the potential patient population.

The investigator or his/her delegated representative will explain to the subject, or his/her legally authorized representative, the aims, methods, anticipated benefits, and potential hazards of the study before any protocol-specific screening procedures or any IP(s) is/are administered, and answer all questions regarding the study.

Subjects must be informed that their participation is voluntary. Subjects or their legally authorized representative (defined as an individual or other body authorized under applicable law to consent, on behalf of a prospective subject, to the subject's participation in the clinical study) will then be required to sign a statement of informed consent that meets the requirements of 21 CFR 50, local regulations, ICH guidelines, Health Insurance Portability and Accountability Act requirements, where applicable, and the IRB/IEC or study site.

Date: 21 April 2022 Page 78 of 108

The medical record must include a statement that written informed consent was obtained before the subject was enrolled in the study and the date the written consent was obtained. The authorized person obtaining the informed consent must also sign the ICF.

The acquisition of informed consent is to be documented in the subject's medical records, and the ICF is to be signed and personally dated by the subject or a legally acceptable representative and by the person who conducted the informed consent discussion. Subject withdrawal of consent or discontinuation from study treatment and/or procedures must also be documented in the subject's medical records; refer to Section 7.

Subjects must be re-consented to the most current version of the ICF(s) during their participation in the study.

The original signed ICF is to be retained in accordance with institutional policy, and a copy of the ICF(s) must be provided to the subject or the subject's legally authorized representative. If a potential subject is illiterate or visually impaired and does not have a legally acceptable representative, the investigator must provide an impartial witness to read the ICF to the subject and must allow for questions. Thereafter, both the subject and the witness must sign the ICF to attest that informed consent was freely given and understood. (Refer to ICH GCP guideline, Section 4.8.9).

A subject who is rescreened is not required to sign another ICF if the rescreening occurs within 21 days from the previous ICF signature date.

The ICF will contain a separate section that addresses the use of all data collected by the digital health tools for optional future research. The investigator or authorized designee will explain to each subject the objectives of the future research. Subjects will be told that they are free to refuse to participate and may withdraw their agreement at any time and for any reason during the storage period. A separate signature will be required to document a subject's agreement to allow any collected data to be used for future research. Subjects who decline to participate will not provide this separate signature.

Data Protection/Subject Confidentiality

The investigator must ensure that the subject's confidentiality is maintained for documents submitted to Amgen.

Date: 21 April 2022 Page 79 of 108

Subject will be assigned a unique identifier by the sponsor. Any subject records or datasets that are transferred to the sponsor will contain the identifier only; subject names or any information which would make the subject identifiable will not be transferred.

On the case report form (CRF) demographics page, in addition to the unique subject identification number, include the age at time of enrollment.

For SAEs reported to Amgen, subjects are to be identified by their unique subject identification number, initials (for faxed reports, in accordance with local laws and regulations), and age (in accordance with local laws and regulations).

Documents that are not submitted to Amgen (eg, signed ICFs) are to be kept in confidence by the investigator, except as described below.

In compliance with governmental regulations/ICH GCP Guidelines, it is required that the investigator and institution permit authorized representatives of the company, of the regulatory agency(s), and the IRB/IEC direct access to review the subject's original medical records for verification of study-related procedures and data. Direct access includes examining, analyzing, verifying, and reproducing any records and reports that are important to the evaluation of the study.

The investigator is obligated to inform and obtain the consent of the subject to permit such individuals to have access to his/her study-related records, including personal information.

Publication Policy

To coordinate dissemination of data from this study, Amgen may facilitate the formation of a publication committee consisting of several investigators and appropriate Amgen staff, the governance and responsibilities of which are set forth in a Publication Charter. The committee is expected to solicit input and assistance from other investigators and to collaborate with authors and Amgen staff, as appropriate, as defined in the Publication Charter. Membership on the committee (both for investigators and Amgen staff) does not guarantee authorship. The criteria described below are to be met for every publication.

Authorship of any publications resulting from this study will be determined on the basis of the Uniform Requirement for Manuscripts Submitted to Biomedical Journals International Committee of Medical Journal Editors Recommendations for the Conduct of Reporting, Editing, and Publications of Scholarly Work in Medical Journals, which states:

Date: 21 April 2022 Page 80 of 108

Authorship credit is to be based on: (1) substantial contributions to conception and design, acquisition of data, or analysis and interpretation of data; (2) drafting the article or revising it critically for important intellectual content; (3) final approval of the version to be published; and (4) agreement to be accountable for all aspects of the work in ensuring that questions related to the accuracy or integrity of any part of the work are appropriately investigated and resolved. Authors need to meet conditions 1, 2, 3, and 4.

When a large, multicenter group has conducted the work, the group is to identify the individuals who accept direct responsibility for the manuscript. These individuals must fully meet the criteria for authorship defined above. Acquisition of funding, collection of data, or general supervision of the research group, alone, does not justify authorship. All persons designated as authors must qualify for authorship, and all those who qualify are to be listed. Each author must have participated sufficiently in the work to take public responsibility for appropriate portions of the content. All publications (eg, manuscripts, abstracts, oral/slide presentations, book chapters) based on this study must be submitted to Amgen for review. The Clinical Trial Agreement among the institution, investigator, and Amgen will detail the procedures for, and timing of, Amgen's review of publications.

Investigator Signatory Obligations

Each clinical study report is to be signed by the investigator or, in the case of multicenter studies, the coordinating investigator.

The coordinating investigator, identified by Amgen, will be any or all of the following:

- A recognized expert in the therapeutic area
- An Investigator who provided significant contributions to either the design or interpretation of the study
- An Investigator contributing a high number of eligible subjects

Data Quality Assurance

All subject data relating to the study will be recorded on printed or electronic CRF unless transmitted to the sponsor or designee electronically (eg, laboratory data, centrally or adjudicated data). The investigator is responsible for verifying that data entries are accurate and correct by physically or electronically signing the CRF.

The investigator must maintain accurate documentation (source data) that supports the information entered in the CRF.

Date: 21 April 2022 Page 81 of 108

The investigator must permit study-related monitoring, audits, IRB/IEC review, and regulatory agency inspections and provide direct access to source data documents.

The sponsor or designee is responsible for the data management of this study including quality checking of the data.

Clinical monitors will perform ongoing source data verification to confirm that data entered into the CRF by authorized site personnel are accurate, complete, and verifiable from source documents; that the safety and rights of subjects are being protected; and that the study is being conducted in accordance with the currently approved protocol and any other study agreements, ICH GCP, and all applicable regulatory requirements per the sponsor's monitoring plan.

The investigator agrees to cooperate with the clinical monitor to ensure that any problems detected in the course of these monitoring visits, including delays in completing CRFs, are resolved.

The Amgen representative(s) and regulatory authority inspectors are responsible for contacting and visiting the investigator for the purpose of inspecting the facilities and, upon request, inspecting the various records of the clinical study (eg, CRFs and other pertinent data) provided that subject confidentiality is respected.

In accordance with ICH GCP and the sponsor's audit plans, this study may be selected for audit by representatives from Amgen's Global Research and Development Compliance and Audit function (or designees). Inspection of site facilities (eg, pharmacy, protocol-required therapy storage areas, laboratories) and review of study-related records will occur to evaluate the study conduct and compliance with the protocol, ICH GCP, and applicable regulatory requirements.

Retention of study documents will be governed by the Clinical Trial Agreement.

All written information and other material to be used by subjects and investigative staff must use vocabulary and language that are clearly understood.

Source Documents

The investigator is to maintain a list of appropriately qualified persons to whom he/she has delegated study duties. All persons authorized to make entries and/or corrections on CRFs will be included on the Amgen Delegation of Authority Form.

Source documents provide evidence for the existence of the subject and substantiate the integrity of the data collected. Source documents are filed at the investigator's site.

Date: 21 April 2022 Page 82 of 108

Source documents are original documents, data, and records from which the subject's CRF data are obtained. These include but are not limited to hospital records, clinical and office charts, laboratory and pharmacy records, diaries, microfiches, radiographs, and correspondence. Source documents may also include data captured in the CRF entries if the CRF is the site of the original recording (ie, there is no other written or electronic record of data, such as paper questionnaires for a patient reported outcomes [PRO]).

Data reported on the CRF or entered in the electronic CRF that are transcribed from source documents must be consistent with the source documents or the discrepancies must be explained. The investigator may need to request previous medical records or transfer records, depending on the study. Also, current medical records must be available.

The Investigator and study staff are responsible for maintaining a comprehensive and centralized filing system of all study-related (essential) documentation, suitable for inspection at any time by representatives from Amgen and/or applicable regulatory authorities.

Elements to include:

- Subject files containing completed CRFs, ICFs, and subject identification list
- Study files containing the protocol with all amendments, Investigator's Brochure, copies of prestudy documentation, and all correspondence to and from the IRB/IEC and Amgen
- Investigational product-related correspondence including Proof of Receipts,
 Investigational Product Accountability Record(s), Return of Investigational Product for Destruction Form(s), Final Investigational Product Reconciliation Statement, as applicable
- Medical device documentation, as applicable

Retention of study documents will be governed by the Clinical Trial Agreement.

Study and Site Closure

Amgen or its designee may stop the study or study site participation in the study for medical, safety, regulatory, administrative, or other reasons consistent with applicable laws, regulations, and GCP.

Date: 21 April 2022 Page 83 of 108

Both Amgen and the Investigator reserve the right to terminate the Investigator's participation in the study according to the Clinical Trial Agreement. The investigator is to notify the IRB/IEC in writing of the study's completion or early termination and send a copy of the notification to Amgen.

